6.0 CLINICAL AND LABORATORY EVALUATION

6.1 Table 1: CCTG 594 Schedule of Events

Schedule of Evaluations				On Study Evaluations									
	Screen	Wk 01	Mo 1 ²	Mo 2 ²	Mo 3 ²	Every 3 months	Mo 4 ²	Mo 5 ²	Mo 6 ²	Mo 12	Every 12 Months ⁵	Primary Endpoint	EOS Assessment
Informed Consent	X												
Medical History	X												
Examination (targeted)										X	X	X	
Randomizati on		X											
HIV RNA		X^4				X^4				X^4	X^4	X^4	
CD4 cell counts		X ⁴				X ⁴				X ⁴	X ⁴	X^4	
ALERT Specialist retention modules ³			X	X	X		X	X					
Plasma Storage		X								X	X	X	
Subject self- reported Assessments		X								X	X	X	
Data abstraction (via chart review, no visits)		X				X			X	X	X	X	
In person or phone call													X

¹ Entry must be within 30 days of screening

EOS – End of Study

Figure 2: Detailed flow diagram of CCTG 594 with scheduled events

CCTG 593 n = 600

Legend:

Blue Dot: ALERT Specialist Red Dote: Study Coordinator

² Planned for monthly intervals but can be done at patient's convenience during course of first year ³ Interventions only for those in ALERT specialist arm

⁴ Abstracted from chart review

⁵ annual visits and annual labs should occur within a window of +/- 60 days from the due date. Labs and study visit do not need to occur on the same day.

6.2 Definitions for Schedule of Events – Timing of Evaluations

6.2.1 *Screening Assessment*

Screening visit must occur within 60 days, the patient's first primary care visit (for patients new to care) or their first primary care re-entry visit (for patients returning to care).

A PID will be assigned to each patient screened for the study. PID's should not be reassigned even if the patient fails to enter the study. The PID must be included on every CRF and patient blood sample. Each site must maintain a master list of PID's in a central location. The patient registration and inclusion/exclusion CRF must be completed on the online system.

Screening will be conducted by the study coordinator, Alert specialist or a trained member of the study team and will include medical history, confirmation of HIV test results, evaluation of Inclusion/Exclusion criteria, and signing of study consent form.

Patients who meet the study eligibility but decline to participate will be offered participation in a brief refusal survey. Patients who verbally consent to participate in the refusal survey will be administered the questionnaire in written or verbal format. Patients who were not previously offered will be re-approached while attending their Primary Care clinic visit and will be offered participation in the brief refusal survey.

6.2.2 Entry Evaluations and Randomization

Entry must occur within 60 days of the patient's first primary care visit (for patients new to care) or their first primary care re-entry visit (for patients returning to care). At study entry, baseline surveys will be collected utilizing the web-based, computer-assisted system on the study specific portal (to view baseline survey, see Attachment 5, *iPad Assessments for CCTG 594*). The portal will allow private completion of questionnaires without concern that clinic or study personnel can view the subject's responses in order to encourage candor.

Subjects will be randomized (1:1) to SOC or ALERT Intervention study arm. Randomization will be stratified by clinic site and whether the subject is newly diagnosed or returning to care. A total of 300 subjects

(150 per arm) will be randomized and followed for a minimum of 48 weeks. SOC will be the clinic standard.

Samples of plasma will be stored for future assays.

6.2.3 On-Study Evaluations

Study specific follow-up visits for each subject will be kept to a minimum in order not to bias the outcome of lost to follow up. Our experience suggests that involvement in a research protocol, with the extra effort the coordinators exert to ensure study follow-up, could easily impact on attendance to clinical care. Thus, for SOC patients, study specific visits will occur yearly preferably in conjunction with a regularly scheduled clinic visits (see below, *yearly study visits*).

In the ALERT intervention arm, the ALERT specialist will conduct 5 monthly educational retention modules (in person or by phone). The ALERT specialist will also continuously monitor and track all health care visits to ensure healthcare continuity, and will intervene using described tools/methods when the subject does not have a visit within a predetermined interval (see Attachment 4, *Manual of Operating Procedures*, for ALERT Specialist job description, methods, and Retention Modules).

6.2.4 Data Abstraction

It is expected that subjects new or returning to care will have regular primary care visits at least 3-4 times in the first year. The ALERT specialist will use the clinic medical record system to abstract data on clinic visits, ART medications, serial HIV RNA and CD4 values, routine CBC and chemistry values, HIV-related and AIDS diagnoses and other medical diagnoses. Data will be entered into the study electronic database. Abstraction will be done at least quarterly for each subject. The ALERT specialist will track the status of each subject and record retention and outreach in the study database. Using data abstracted from the primary care clinic medical records system, the ALERT specialist will record all visits with a prescribing HIV provider, which will document retention as related to the primary study endpoint. For patients in the SOC arm, contact information will be collected for use in the event that the person meets the primary endpoint. Subjects in either arm who reach criteria for the LTFU primary endpoint will be identified by the ALERT specialist. The ALERT specialist will then contact the subject to assure that the patient is not incarcerated or receiving care from an HIV provider at

another facility. Once LTFU is confirmed, the ALERT worker will try to bring the patient in for a primary endpoint visit. All patients will continue to be followed after the primary endpoint (ITT) for assessment of secondary endpoints.

Education Contacts (weeks 1-24). The ALERT specialist will complete a 5 session educational curriculum called a retention module either in person or by phone to the subjects randomized to the ALERT Intervention arm. The 5 retention modules include instruction about the navigation of HIV health systems, HIV literacy, Disclosure, Medication adherence and Continuation with Care, and Self-Efficacy [MOP CCTG 594: 5.0 The 5 Retention Modules for the ALERT specialist]. The goal will be to present the majority of the material within the first 6 months, however scheduling flexibility will be allowed up to the 12 month time-point in order to maximize opportunities for patients to receive the intervention. Subjects that complete all 5 modules will be asked about their reasons motivating them to 1) participate in the study and 2) completing the 5 modules.

Ongoing Retention Efforts. The ALERT specialist will continuously monitor visit records on all patients in the ALERT specialist Intervention arm and will utilize all tools developed for clinic specific re-engagement to aggressively track, find, and re-engage patients during the study. Monitoring will include missed visits and intervals between scheduled visits. In addition to continuous monitoring for missed appointments, the ALERT specialist will screen the charts of all enrolled subjects every 3 months to evaluate the number of clinic contacts, missed visits, missed attendance of the retention modules, and any other risks for falling out of care.

Yearly Study Visits. For both arms, a study-specific visit will be conducted at yearly intervals from the enrollment date. The annual visits must occur within a 60 day window before or after the due-date. At the annual study visits the baseline study assessments will be repeated along the collection of plasma which will be stored for future assays. Efforts will be made to have these study visits occur around a regularly scheduled clinic visit.

Though every effort will be made to bring all patients in for annual visits within the 60 day window, subjects may remain in the study if the annual visit is missed (i.e., not completed within the 60 day window).

Compensation. Study participants will be compensated for their time at intake, annual, and endpoint visits which are anticipated to require 1-2 hours for questionnaires and collection of lab specimens.

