The ALERT specialist will be responsible for tracking the on-going engagement of patients who are randomized into the intervention arm. Patients will be expected to complete visits at a minimum of every 6 months. However, the ALERT specialist will also review chart notes to review the interval that the provider recommended a medical visit. The ALERT specialist will track that the patient makes and keeps an appointment with their primary provider at the suggested interval. If the patient misses a visit at the recommended interval, the ALERT specialist will perform outreach to schedule a return visit, and again track to see that the visit is kept. The ALERT specialist will use a tracking database in order to track patient engagement, their outreach efforts and delivery of the retention modules. The ALERT specialist will record contacts (categorically) both successful and unsuccessful. They will also utilize the baseline patient contact information as well as other key notes in this tracking database. Patients who meet the LTFU primary end point, regardless of study arm will have outreach activity initiated by the ALERT specialist. This will include following the retention tracking algorithm including evaluating whether the patient is incarcerated, providing outreach calls to the patient, and reviewing the medical record. Patients who meet the primary endpoint and are found to be incarcerated will be removed from the study and censored effective at the time of their incarceration. Those who are incarcerated but then return to care upon release, prior to reaching a primary endpoint will be allowed to remain in study. Patients who are confirmed to have changed care provider to an external health facility (such as a different clinic system or a nursing facility) will be assessed for their current engagement in care; those who have completed a clinic visit with a HIV prescribing clinician within the 180 days will be considered engaged in care, and will not be considered LTFU. The ALERT specialist will request access to the patient's new HIV prescribing provider in order to assess continued follow-up care during the course of the study. In addition, if possible, these patients will continue to come to study site for the annual study visit.

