9.4 Sample Size and Accrual

9.4.1 Power and Sample Size Justification

The primary outcome for this study is to compare the time to LTFU. A secondary outcome is time to initiation of ART. Sample size calculations were based on a two-sided, two-sample log-rank test to compare the differences in time to the-primary endpoint proportions between the intervention arm and the standard of care arm.

Since attrition is a component of the composite endpoint, attrition rates are not used as an adjustment in the power calculations. Assuming 150 subjects per group in each of the two

Table 5: Power based on a two-sided, log-rank test with alpha=0.05 and N=150 per arm (total N = 300)							
Composite	Composite rate	Corresponding	Statistical				
rate without	without	Hazard Ratio	Power (%)				
Endpoint in	Endpoint in	(HR)					
SOC (%)	Intervention						
	(%)						
65	80	1.93	82				
65	85	2.65	97				
70	85	2.19	87				
75	87.5	2.15	78				
75	90	2.73	92				
80	92.5	2.86	87				
80	95	4.35	97				

groups (for a total of 300 subjects), we have 87% power to detect a difference of 15%, assuming a time without a composite endpoint rate of 70% in SOC arm and that the intervention arm will increase the time without an endpoint (to a rate to 85%). This corresponds to a hazard ratio of 2:19. Table 5 shows other possible standard of care rates between arms (and hazard ratios), and corresponding statistical power. The calculations assume that the hazard rates are proportional.

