9.6.2 Analysis of Primary Outcome

A survival analysis of "time to LTFU" will be conducted. LTFU is defined as no visit with a prescribing HIV provider in the last 180 days. Time-to-LTFU will be calculated as total days between the first visit and the date when the participant reaches the definition of LTFU.

For example, a subject has his first visit on Jan 1, 2013, and another visit on Mar 1, 2013. If the subject does not have any visits thereafter, or does not have any visits until >180 days later, the subject will be counted as reaching the primary endpoint of LTFU. In this case, the subject would be LTFU if no visit occurred before Aug 27, 2013, (which is 180 days past Mar 1st). The "time-to-LTFU" will be the time period between Jan 1, 2013 and Aug 27, 2013.

At the end of the study, patients who have not reached the primary endpoint will be censored at the time of their last quarterly data extraction.

Patients who meet the primary endpoint and are found to be incarcerated will be removed from the study and censored effective at the time of their incarceration. Those who are incarcerated but return to care upon release, prior to reaching a primary endpoint, will be allowed to remain in study. Patients who change care provider to an external health facility (such as a different clinic system or a nursing facility) will be assessed for their current engagement in care; those who have completed a clinic visit with a prescribing clinician within the 180 days will be considered engaged in

care, and will not be considered LTFU. If possible, these patients will continue to come in for annual study visits.

The null hypothesis is that the median time-to-LTFU estimated using the Kaplan-Meier method will be identical in both groups. The log-rank test will be used to test the null hypothesis against the alternate hypothesis that the median time-to-LTFU is not the same between the groups.

In addition, to assess the factors associated with time-to-LTFU, Cox regression models will be performed on two subgroups, looking at each arm separately. The model will have time to LTFU as the outcome, baseline variables such as demographic, socioeconomic, psychosocial factors, risk behavior, substance use and psychiatric illness as predictors.

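### The unblinded ALERT specialist who delivers the intervention also makes the contact that can cancel an LTFU event, so uneven confirmation of transfers could tilt the primary comparison toward ALERT

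*Combined protocol and SAP*

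**What the plan says.** Section 9.1 describes an unblinded two-arm trial. Under section 6.2.3 the ALERT specialist delivers the five modules and the outreach. Under section 6.2.4 the same specialist abstracts the prescriber visits that document the primary endpoint, and "Subjects in either arm who reach criteria for the LTFU primary endpoint will be identified by the ALERT specialist". The specialist then contacts the patient to rule out incarceration and HIV care at another facility. LTFU counts as confirmed after that, but the text does not say who confirms it.

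Two findings change the outcome. "Patients who are confirmed to have changed care provider to an external health facility" are assessed for current care (section 5.1.4), and section 9.6.2 says "those who have completed a clinic visit with a prescribing clinician within the 180 days will be considered engaged in" care and so not LTFU. Incarceration found at the endpoint turns the event into a censoring at the date of incarceration.

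Contact before the endpoint differs by arm. "The ALERT specialist will continuously monitor visit records on all patients in the ALERT specialist Intervention arm" (section 6.2.4, ongoing retention efforts), and these patients also have up to five module contacts and follow-up of missed visits. SOC contact details are gathered at entry and kept for use if the endpoint is met.

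Several procedures are common to both arms: the baseline contact form (section 5.1.2), chart abstraction at least quarterly and annual study visits (section 6.2.4), and specialist outreach once LTFU criteria are met (section 5.1.4).

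**The concern.** A gap of more than 180 days in the clinic record is an event unless someone learns that the patient is in care elsewhere. Learning this depends partly on reaching the patient or the new provider. The text sets no number of attempts, requires no particular outside record, and has no rule for a patient who cannot be reached, so an unconfirmed transfer stays an LTFU event.

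If transfers are confirmed more often in ALERT, more events are cancelled there and the log-rank test sees a retention benefit that does not exist. The person making the check knows the arm and delivers the intervention. Section 6.2.3 already limits study visits so that research contact does not distort LTFU. That protects attendance, but it does not address how well LTFU is ascertained. Section 9.6.2 has no analysis that would show whether a positive result depends on these cancellations.

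**Working it through.** **The plan's own figure.** Section 9.4.1, Table 5: "Power based on a two-sided, log-rank test with alpha=0.05 and N=150 per arm (total N = 300"). The main case: "we have 87% power to detect a difference of 15%, assuming a time without a composite endpoint rate of 70% in SOC arm" and 85% in the intervention arm.

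- HR = ln(0.70)/ln(0.85) = 2.195 (plan: 2.19).
- Expected events D = 150 × (0.30 + 0.15) = 67.5.
- Freedman: z = √D × (HR − 1)/(HR + 1) = 8.216 × 1.195/3.195 = 3.07. Power = Φ(3.07 − 1.96) = 86.7% (plan: 87%).

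The power figure reproduces and is not in dispute. The same formula can size the bias.

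**Inputs for the bias.** From the plan: 150 per arm, two-sided 0.05, 30% LTFU in SOC. Assumed, because the plan gives no values: the share *s* of patients who transfer and are in care elsewhere, and the probabilities *c* that this is confirmed in each arm. True LTFU *L* is the same in both arms (no effect). Confirmed transfers are treated as event-free.

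Two versions bracket the result:
- Version A: L = 25%, transfers separate from true LTFU. P(event) = L + s(1 − c).
- Version B: L = 30% (the plan's SOC rate), transfers independent of LTFU. P(event) = L + (1 − L)s(1 − c).

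**Worked case: s = 10%, c = 90% ALERT against 50% SOC.**
- A: 0.25 + 0.10 × 0.1 = 0.260 against 0.25 + 0.10 × 0.5 = 0.300. HR = ln(0.700)/ln(0.740) = 1.185; D = 84; z = 0.77. Rejection = Φ(0.77 − 1.96) + Φ(−0.77 − 1.96) = 12.1%.
- B: 0.30 + 0.70 × 0.10 × 0.1 = 0.307 against 0.30 + 0.70 × 0.10 × 0.5 = 0.335. HR = 1.112; D = 96.3; z = 0.52. Rejection = 8.2%.

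**Two-sided rejection with no true effect (nominal 5%), versions B to A:**

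| Confirmed, ALERT vs SOC | s = 5% | s = 10% | s = 15% | s = 20% |
|---|---|---|---|---|
| 90% vs 50% | 5.8–6.8% | 8.2–12.1% | 12.2–20.8% | 17.7–32.4% |
| 90% vs 70% | 5.2–5.5% | 5.8–6.8% | 6.8–8.9% | 8.1–12.0% |
| 90% vs 80% | 5.0–5.1% | 5.2–5.4% | 5.4–6.0% | 5.8–6.7% |

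Simulated log-rank tests agree with these to about one percentage point; for 90% against 50% they gave about 8–11% at s = 10% and 17–32% at s = 20%. Equal confirmation gives about 5%.

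**Direction.** For 90% against 50%, at least 92% of rejections favour ALERT once s is 10% or more, and 77–86% at s = 5%. For 90% against 70% the figures are 77–97% at s of 10% or more and 65–72% at s = 5%.

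**In patients.** In version A the expected surplus of SOC events is 150 × s × (difference in c). At s = 10% and a 40-point difference that is 150 × 0.10 × 0.40 = 6; at s = 20% it is 12. Starting from 45 events in each arm, cancelling 15 more in ALERT alone gives 30 against 45: HR = ln(0.70)/ln(0.80) = 1.60, D = 75, z = 1.99, which is nominally significant with no effect.

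**The case against.** The strongest reply is that the endpoint is a date rule with a worked example, and that cancelling it requires a completed visit to an outside prescriber, which is a fact rather than a judgement. The contact form, quarterly chart abstraction, annual visits and endpoint outreach cover both arms, and the check already starts from the same trigger. All of this stands. It narrows the concern to differences in prior contact and tracking, and to knowledge of the arm.

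Three stronger readings are tempting, and the documents do not support them:
- That the specialist alone decides which events are cancelled. The text has the specialist identify and contact; sole authority is only an inference from no one else being named.
- That in SOC the specialist has nothing but an entry contact sheet. The procedures common to both arms contradict this.
- That a false-positive rate near one third is to be expected. That needs a 20% transfer share, a 40-point confirmation gap and transfers that never overlap with LTFU, none of which comes from the plan. Confirmed transfers can also become LTFU later, since section 5.1.4 has the specialist follow their care with the new provider; this would dilute the bias.

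Section 9.0 also defers to a fuller SAP that takes precedence, and the search procedures are in the Manual of Operating Procedures. Neither is in the supplied text, and either may hold some of what is missing here.

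**Conclusion.** The concern holds as a possible bias and calls for a cheap improvement; the documents do not show that the primary result will be wrong. As supplied, the plan gives the endpoint check to unblinded intervention staff who have more prior contact with one arm, with no independent review and no analysis that removes the cancellations.

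The size cannot be known from the documents. Under the stated assumptions, type I error reaches about 8–12% with a 10% transfer share and 90% against 50% confirmation, and 17–32% with a 20% share. It is about 5–12% at 90% against 70%, and about 5–7% at 90% against 80%. Material inflation therefore needs both frequent transfers and a wide confirmation gap. The direction is mostly toward ALERT at shares of 10% or more and less clear at 5%. The incarceration rule has the same weakness, but its effect was not sized.

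**What to change.** 1. The data unit derives the 180-day gap and the event date by program from the abstracted visit dates, identically in both arms.
2. At the existing LTFU trigger, the outside-care and incarceration checks use the same number of attempts and the same sources in both arms. The study coordinator, who is not assigned to deliver the modules, makes them in place of the ALERT specialist. This does not blind the check, because the coordinator may also perform the randomization (section 9.3).
3. Section 9.6.2 adds a sensitivity log-rank analysis on clinic-record LTFU that ignores outside-care cancellations in both arms. Cancellations and incarceration censorings are reported by arm.

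The cost is some SAP wording, one more log-rank run, and a task moved to existing staff. Step 3 alone needs no new staff or data. Its drawback is that true transfers count as events in both arms, so it should be read beside the primary analysis and not in place of it.

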6.2.5 Primary endpoint visit

When a participant reaches the primary endpoint of LTFU, every effort will be made to return the participant for an endpoint study visit. If the patient is willing, this visit will include the same assessments and procedures as the annual study visits.

6.3 Special Instructions and Definitions of Evaluations

6.3.1 Documentation of HIV

Documentation of HIV-1 infection will be confirmed by reviewing a positive test from any licensed screening antibody test, such as ELISA, and confirmed by a second antibody test, such as Western blot, or detectable plasma HIV-1 RNA at any time prior to study entry. If an ELISA or Western Blot is not available, HIV infection may be documented by two HIV RNA values \geq 2000 copies/mL, drawn at least 24 hours apart. The RNA assays should have been run at CLIA approved laboratory or equivalent.

6.3.2 *Medical and Laboratory History*

At screening, a medical history will be obtained and must be recorded in the source documents. The medical history should include any previous HIV-related diagnoses, malignancies, and AIDS-defining events which will be recorded on the electronic CRF. History will include date of HIV diagnosis, date of last HIV clinic visit (for those returning to care), antiretroviral (ARV) history (if any), concomitant medical conditions, substance use history.

6.3.3 *Medication History*

At screening, a medication history (only of those taken within the last 30 days prior to entry) with actual or estimated start and stop dates should be obtained and recorded in the source documents and the concomitant medication CRF, including:

All prescription medications, including medications taken for the

treatment or prophylaxis of opportunistic infections.

- Non-prescription medications.
- Alternative therapies and/or dietary supplements.
- Allergies to any medications and their formulations must be documented.

